3.2 Sample size determination and power calculations

The primary aim of this study is to determine whether short-course antimicrobial therapy (five days) is non-inferior to standard-of care antimicrobial therapy (10

days) for the treatment of UTI in children with respect to reinfection of UTI through TOC visit Day 11-14. The treatment failure rate under the standard of care, R_0 , is expected to be 5%. This estimate is based on data from previously published studies [1, 2]. The power and sample size calculations are based on the assumption that recurrence under the short-course therapy, R_{SC} , will range from 5% to 9%.

In the non-inferiority test, on which power and sample size are based, the null hypothesis that short-course therapy is inferior to standard-of-care therapy is tested against the alternative that short-course therapy is non-inferior. That is, $H_0: R_{SC} > R_0 + \delta$ is tested against $H_a: R_{SC} \leq R_0 + \delta$, where δ is the “interval of equivalence,” the range in which the treatment failure rates of the two therapies would be considered clinically equivalent. We believe that an interval of equivalence of 5% would be clinically acceptable; a success rate of 95% for the standard-of-care therapy group when compared to 90% for the short-course therapy group. For all power and sample size calculations, the significance level (chance of incorrectly rejecting the null hypothesis) is $\alpha = 0.05$.

Table 1 gives the power for testing the non-inferiority hypothesis with a sample size of 300 evaluable subjects per arm and with equivalence intervals (i.e., δ) ranging from 2% to 5%. With 300 subjects per arm, there would be 87% power with $R_{SC} = 5\%$ and $\delta = 5\%$. The power decreases as either the equivalence interval decreases or as R_{SC} increases; in other words, as the recurrence rates of the two regimens become more similar, large sample sizes are required to discriminate between them.

Table 2 gives the sample sizes required to obtain 80% power with the same parameters for R_{SC} and δ . A sample size of 235 per arm is sufficient for 80% power with $R_{SC} = 5\%$ and $\delta = 5\%$, while larger sample sizes are required for larger values of R_{SC} or smaller values of δ . Finally, Table 3 gives the sample sizes required to obtain 90% power; a sample size of 326 subjects per arm would be required for 90% power with $R_{SC} = 5\%$ and $\delta = 5\%$.

Table 1: Power (%) for comparing standard and shortened treatment for UTI

Interval of equivalence	Recurrence rate under shortened treatment				
	5%	6%	7%	8%	9%
2%	30	13	–	–	–
3%	51	28	12	–	–
4%	72	48	27	12	–
5%	87	69	46	25	12

Notes: Values for power in the table are given in percent and were calculated for comparing rates of recurrence between standard and shortened treatment for UTI, with sample sizes of 300 per arm and an assumed significance level of 0.05. The assumed recurrence rate for standard treatment is 5%. As an example, if the actual recurrence rate for shortened treatment is 6%, there is 28% power for finding non-inferiority with an equivalence interval of 3%. However, the power increases to 69% with an equivalence interval of 5%.

Table 2: Sample sizes for 80% power for non-inferiority of shortened vs. standard UTI antibiotic regimen

Interval of equivalence	Recurrence rate under shortened treatment				
	5%	6%	7%	8%	9%
2%	1,469	6,424	–	–	–
3%	653	1,606	6,962	–	–
4%	368	714	1,741	7,488	–
5%	235	402	774	1,872	8,001

This table gives sample sizes PER ARM for achieving 80% power for testing non-inferiority under the given values for recurrence rates and equivalence intervals. The significance level is assumed to be 0.05. The assumed recurrence rate for standard treatment is 5%. As an example, 653 study participants per arm (1,306 total) would be required for 80% power if the recurrence rate for the standard of care and shorted regimens were both 5%, with an equivalence interval of 3%.

Table 3: Sample sizes for 90% power for non-inferiority of shortened vs. standard UTI antibiotic regimen

Interval of equivalence	Recurrence rate under shortened treatment				
	5%	6%	7%	8%	9%
2%	2,034	8,898	–	–	–
3%	904	2,225	9,643	–	–
4%	509	989	2,411	10,371	–
5%	326	557	1,072	2,593	11,082

This table gives sample sizes PER ARM for achieving 90% power for testing non-inferiority under the given values for recurrence rates and equivalence intervals. The significance level is assumed to be 0.05. The assumed recurrence rate for standard treatment is 5%. As an example, 509 study participants per arm (1,018 total) would be required for 90% power if the recurrence rate for the standard of care and shortened regimens were both 5%, with an equivalence interval of 4%.

Based on these calculations, we propose a sample size of 326 per arm. However, this value must be adjusted upwards to offset loss to follow-up. It is expected that loss to follow-up will be minimal in this study. Because the study is of short duration, we are hopeful that we will be able to follow virtually all subjects to study completion. However, some study participants will not return for the follow-up visits to determine the primary endpoint. Furthermore, some percentage may need to disrupt or discontinue study treatment, or may not have the endpoint determined due to problems with specimens or laboratory processing. Altogether, these factors may reduce the sample size by as much as 10%. Thus we propose to increase the sample by approximately 11% to offset this sample size reduction, resulting in the final proposed sample size of 362 study participants per arm.

4. Statistical Analyses

The methods for the planned statistical interim analysis including the timing of the interim analysis, the scope of the interim analysis (a description of which endpoints will be analyzed), and the methods or statistical tests that will be used in the interim

analysis are described. The general description of the planned final analysis is provided.

4.1 Interim Analysis

After half of the subjects (373 subjects) have enrolled, an interim analysis for the primary endpoint of treatment failure rate will be performed. This efficacy analysis will test the null hypothesis that the treatment failure rate under short-course therapy is less than or equal to that of standard-of-care therapy; the alternative hypothesis is that the failure rate under short-course therapy is greater than using standard-of-care therapy. This test will be one-sided test of hypothesis of equal treatment failure rates between the short-course therapy and standard-of-care therapy with $\alpha=0.05$. We will calculate the difference in treatment failure rates between short-course therapy and standard-of-care therapy, and a one-sided 95% lower confidence limit using normal approximation for large samples. If the lower confidence limit exceeds zero, we will conclude that short-course therapy has a significantly higher failure rate than standard-of-care therapy. Since the interim analysis is for superiority of standard-of-care therapy and the final efficacy analysis is for non-inferiority of short-course therapy, there is no impact of the interim analysis on the Type I error of the final efficacy analysis and thus no adjustments to the significance level are required.

In addition, conditional power estimates may be calculated. The conditional power analysis is a re-assessment of the power given the results of the study to date. If the recurrence rate for short course therapy is smaller than expected relative to standard therapy, then there would be high conditional power; if the recurrence rate for short course therapy is greater than expected relative to standard therapy, then there would be lower power than initially expected. The need for this analysis will be

decided in conjunction with the DSMB, along with other data to be presented to the DSMB.

4.2 Final analyses

The data analysis will consist of several parts. First, descriptive and baseline characteristics will be generated for outcome measures for the purpose of describing the study population and comparing the two study arms at baseline. Second, the primary and secondary analyses will be conducted. Finally, primary and secondary outcome measures will be compared between various subgroups of the study participants to assess potential interactions with treatment effects. Details are provided below.

4.2.1 Descriptive analyses

Standard descriptive statistics will be used to describe subjects' baseline characteristics and study outcome measures overall and within each treatment group. Summary statistics such as means, standard deviations, medians, and ranges will be produced for continuous variables. Frequency counts and percentages will be generated for describing variables that are dichotomous or polytomous in nature. The balance of baseline measures between short-course therapy group and standard-of-care therapy group will be compared using two-sample *t*-tests for normally distributed data or, the Mann-Whitney test for non-normally distributed data and using chi-square tests for categorical variables (*Table 1 and 2 in Section 7.1*).

4.2.2 Primary/Efficacy analysis

The primary endpoint of this study is the proportion of children experiencing treatment failure (symptomatic UTI) at the TOC visit (Day 11-14).

The primary analysis will follow intent-to-treat (ITT) principles, with subjects analyzed according to randomized treatment assignment (*Table 3 in Section 7.1*). In addition, a “per-protocol” analysis will be performed; the per-protocol analysis would include only subjects who were adherent to their assigned study regimen and completed more than 80% of the prescribed dose (*Table 4 in Section 7.1*). All subjects taking at least one dose of study treatment between Day 6 and Day 10 who have been evaluated for treatment success at TOC visit or have failed before TOC will be included in the ITT analysis (See Table 4 below).

The primary analysis will be a non-inferiority test comparing the proportion of children with symptomatic UTIs at the TOC visit between two treatment arms to evaluate whether the difference is within the 5% equivalence interval. This test will be conducted by calculating the one-sided 95% upper confidence limit for the difference in symptomatic UTI (treatment failure) rates between the short-course and standard-of-care therapies. If this limit is less than or equal to the equivalence interval (0.05), then we will conclude that short course therapy is not inferior to standard therapy. Subjects with asymptomatic bacteriuria or who are asymptomatic with a positive culture including pyuria will NOT be considered treatment failures for the primary outcome measure.

Table 4: SCOUT Study Medication Dosage Adherence

Antibiotic Drug	Antibiotic Dosage	80% of Expected Doses
Trimethoprim-Sulfamethoxazole (TMP-SMX)	8 mg/kg/day of Trimethoprim in 2 divided doses, Max 160mg BID Trimethoprim	Eight doses
Amoxicillin-Clavulanate	45 mg/kg/day in 2 divided doses, Max 875 mg Q12H	Eight doses
Cefixime	8 mg/kg/day in 1 dose, Max 400 mg	Four doses
Cephalexin	50mg/kg/day in 3 divided doses	Twelve Doses

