6.4 Treatment Assignment Procedures

6.4.1 Randomization Procedures

The SCOUT Study is a randomized, double-blind, placebo-controlled clinical trial.

After a potential subject has been determined to meet eligibility criteria, the subject will be given a random treatment assignment of study product to either short-course or standard-of-care therapy. Randomization will be done using fixed blocks of size four. Subjects will be stratified (within site) by febrile/non-febrile condition when originally diagnosed and antibiotic prescribed at initiation of therapy. That is, separate randomization sequences will be generated for each site for each of eight strata defined

by febrile/non-febrile condition and the four initially prescribed possible antibiotics. Treatment kits will be pre-packaged and randomized to active or placebo in a 1:1 ratio. Subjects initially prescribed cefdinir will be randomized to either cefixime or cefixime placebo.

The SCOUT Study will employ WesTrax™ an interactive voice response (IVR) system to randomize subjects. This system uses the telephone as a means to input data. Pre-recorded prompts are played listing the various options available to the user or requesting responses to particular questions. Data are entered using the telephone touch-tone keypad and are written to the underlying databases. The Study Nurse/Nurse Practitioner/Physician will randomize the subject based on the responses collected during the call into the system at the Enrollment Visit.

The system security is enforced through the recognition of unique User ID and PIN numbers assigned to each system user. Each PIN number is associated with a list of system privileges.

The Westat staff will train site personnel prior to study enrollment. In addition, at the time of site activation, each user at the activated site will receive an instruction packet. User instructions are project-specific and the packet will contain the necessary instructions for the user's appropriate system access level.

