2.4.2 Randomization and replacement

Children whose parents agree to participate in the study will be randomized to either (1) standard-of-care antimicrobial therapy (10 days of antibiotic therapy) or (2) short course antimicrobial therapy arm (five days of antibiotic therapy). We will stratify randomization within site based on (1) whether the UTI was originally associated with fever, and (2) the antibiotic prescribed at initiation of therapy. After treatment, the subjects will be followed for 38-44 days through follow-up phone calls and study visits. Subjects that withdraw or are withdrawn from the study prior to being evaluable for the primary outcome measure will be replaced. The study will continue until at least 652 subjects are evaluable for the primary outcome measure. At least 724 subjects will be enrolled in order to reach 652 evaluable subjects, but the total number that will be 'enrolled / consented' may exceed 724 if the study has not enrolled 652 evaluable for the primary endpoint.

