7.1 SAP Table shells

Table 1. Randomization review

	Arm 1: Standard Course Total= xxx N (%)	Arm 2: Short Course Total= xxx N (%)
Presence of fever		
Yes		
No		
Antibiotic Type		
TMP-SMX		
Amoxicillin-Clavulanate		
Cefixime		
Cefdinir		
Cephalexin		

Note: Chi-square tests for frequencies across two treatment groups

1. P=0.xxxx for Presence of fever versus No fever
2. P=0.xxxx for Antibiotic Type

Table 2. Demographic and baseline data

	Arm 1: Standard Course Total= xxx N (%)	Arm 2: Short Course Total= xxx N (%)	p-value
Age, Mean ± SD			
2 months -35 months			
3 – 6 years			
7 – 10 years			
Gender			
Male			
Female			
Race/ethnicity			
White			
Black/African American			
Asian			
Native Hawaiian/Other Pacific Islander			
American Indian/Alaska Native			
Multi-Racial			
Other			
Hispanic			
Yes			
No			

Table 2 Specifications

- Repeat the analysis on population 1 (ITT population) and 2 (per-protocol population) separately as Table 2a and 2b.
- Table 2 was designed to show the frequencies and column percentage of subjects within each category unless was specified as to show means and standard deviation. Some categorical variables may need to be created based on numeric values.

Table 3. Comparison of the proportion of subjects with symptomatic UTIs prior to or at the TOC visit for ITT population (Population 1) (Primary analysis)

	Arm 1: Standard Course Total= xxx N (%)	Arm 2: Short Course Total= xxx N (%)	Difference of proportion and one- sided 95% confidence limit
Treatment Failure			

SAS note: Using RISKDIFF ALPHA=0.10 in the TABLE STATEMENT of PROC FREQ procedures to calculate the difference of proportion and one sided 95% CI

Table 4. Comparison of the proportion of subjects with symptomatic UTIs prior to or at the TOC visit for per protocol population (Population 2) (Primary analysis)

	Arm 1: Standard Course Total= xxx N (%)	Arm 2: Short Course Total= xxx N (%)	Difference of proportion and one- sided 95% confidence limit
Treatment Failure			

Table 5. Comparison of the proportion of subjects with a recurrent infection at any time after the TOC visit for per protocol population (Population 3) (Secondary analysis, Endpoint a)

	Arm 1: Standard Course Total= xxx N (%)	Arm 2: Short Course Total= xxx N (%)	Difference of proportion and two- sided 95% confidence limit
Recurrent Infection			

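### Randomisation is stratified by site, fever and antibiotic, but the primary risk difference is crude; a prespecified stratified estimate would be a small, low-cost improvement.

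*SAP*

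**What the plan says.** **Design.** Protocol 6.4.1 states: "Subjects will be stratified (within site) by febrile/non-febrile condition when originally diagnosed and antibiotic prescribed at initiation of therapy". It adds that "separate randomization sequences will be generated for each site for each of eight strata", the eight being two fever categories by four antibiotics, and "Randomization will be done using fixed blocks of size four". With two sites that makes 16 lists. SAP 2.4.2 agrees: "We will stratify randomization within site based on (1) whether the UTI was originally associated with fever, and (2) the antibiotic prescribed". The SAP table shells still carry amoxicillin-clavulanate, now retired, as a fifth antibiotic, so up to 2 x 2 x 5 = 20 cells could hold data.

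**Primary analysis.** SAP 4.2.2 tests non-inferiority by "calculating the one-sided 95% upper confidence limit for the difference in symptomatic UTI (treatment failure) rates between the short-course and standard-of-care therapies" and compares that limit with 0.05. Protocol 12.4 describes the same one-sided comparison. The Table 3 shell in SAP 7.1 has a single row for treatment failure, and its programming note reads "Using RISKDIFF ALPHA=0.10 in the TABLE STATEMENT of PROC FREQ procedures", with no stratification variable. Table 4 (per-protocol) has the same layout. The SAP never calls the analysis unstratified; that follows from the text and the note together.

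**Where the strata do appear.**
- SAP Table 1 checks balance on fever and antibiotic, but not site.
- SAP 4.2.5 and Tables 12 to 17 give exploratory subgroup comparisons by age, fever, antibiotic and site.
- Table 18 is a logistic model for treatment failure. It is fitted only for factors where subgroup differences reach significance, and its covariates are unnamed.

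Neither document gives a reason for leaving the strata out of the primary estimate.

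**The concern.** A trial that stratifies its randomisation has declared those factors important enough to balance. The usual expectation is that the primary analysis uses the same factors, or that the plan says why it does not. Two things are lost otherwise. The standard error of a crude difference includes between-stratum variation that stratified allocation has largely removed, so the limit is a little wider than it need be. And any imbalance remaining among the analysed children is not corrected in the point estimate.

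The estimate concerned is the one that decides non-inferiority. Table 18 does not fill the gap: it is conditional on subgroup findings, and it reports an odds ratio, which cannot be set against a margin of 5 percentage points. If the upper limit fell close to 0.05, a choice between crude and adjusted limits made after unblinding would be open to challenge. The choice therefore belongs in the SAP.

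**Working it through.** **Inputs from the documents.** Control failure rate 5%, margin 5 points, one-sided alpha 0.05, 90% power, 326 per arm (SAP 3.2); 672 evaluable, so 336 per arm (Protocol 5; SAP 2.4.2 has 652, which does not affect the conclusion). Stratum-specific failure rates are not given, so those below are assumptions.

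**1. Reproduce the plan's figure without strata.** With z values 1.645 and 1.282:

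n per arm = 2 x 0.05 x 0.95 x (1.645 + 1.282)² / 0.05² = 0.095 x 8.564 / 0.0025 = 325.4, rounded up to **326**.

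This matches SAP 3.2 and Table 3 of that section. The same formula also returns 235, 402 and 653 (80% power) and 509 and 557 (90% power), as tabulated. Sample size and planned analysis therefore agree with each other.

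**2. Effect of stratifying, analytic.** Under balanced strata, p(1 − p) is replaced by its average over strata. For rates of 1% and 9% in two equal strata: (0.0099 + 0.0819)/2 = 0.0459, against 0.0475 crude. The distance from estimate to upper limit at 336 per arm is 1.645 x √(2 x variance/336).

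| Two equal strata, mean 5% | Variance term | n per arm for 90% power | Power at 336 per arm | Estimate to limit (points) |
|---|---|---|---|---|
| Crude | 0.0475 | 326 | 90.8% | 2.77 |
| 4% / 6% | 0.0474 | 325 | 90.9% | 2.76 |
| 3% / 7% | 0.0471 | 323 | 91.0% | 2.75 |
| 2% / 8% | 0.0466 | 320 | 91.3% | 2.74 |
| 1% / 9% | 0.0459 | 315 | 91.6% | 2.72 |

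The saving is at most 11 children per arm and 0.8 points of power.

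**3. Effect of stratifying, simulated.** 20,000 trials per scenario; 672 children; 16 lists in blocks of four; mean control rate 5%. Assumed mix: sites 60/40, fever categories 60/40, antibiotics 40/25/10/25. The crude large-sample limit is compared with a Mantel-Haenszel risk difference using Sato variance. Type I error is evaluated with the short-course rate 5 points higher in every stratum.

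| Stratum rates | Power, crude | Power, stratified | Type I, crude | Type I, stratified |
|---|---|---|---|---|
| All 5% | 90.5% | 90.6% | 5.4% | 5.5% |
| 1.5% to 14% | 91.0% | 91.3% | 5.0% | 5.2% |
| 0.3% to 27% | 91.7% | 92.8% | 4.8% | 5.5% |

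A separate run with rates from 1.6% to 15.7% gave power of 91.5% crude and 91.9% stratified, with type I error of 5.1% and 5.2%. The Monte Carlo standard error of a 5% rate over 20,000 trials is √(0.05 x 0.95/20,000) = 0.15 points.

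**4. Sparseness.** Expected failures: 0.05 x 672 = 33.6, about 34. Over 16 cells that is about 2.1 per cell, or one per arm per cell; over 20 cells it is 1.7. At the interim, 0.05 x 336 = 16.8, about 17 failures in all.

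**The case against.** The strongest case for leaving the plan alone is that nothing in it is wrong. A crude difference under stratified 1:1 allocation is valid. In a non-inferiority trial a slightly wide limit errs on the safe side. The crude analysis matches the sample-size formula. In the simulations the stratified limit never had the lower type I error, and in the most extreme scenario it ran at 5.5% against 4.8%. With about two failures per cell, full stratification needs a pooling rule, and pooling gives up some of the strata it was meant to respect. All of this stands. It limits the point to a modest improvement, and it is why the pooling rule is an essential part of the fix.

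Three stronger readings are tempting, and the documents support none of them.

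- **The sites' laboratories differ (Protocol 9.2.1), so a crude analysis is biased.** Allocation is blocked within site, so laboratory differences fall on both arms alike. The culture thresholds that define failure are common to both sites.
- **Losses after randomisation break the balance in a biasing way.** Entry failures occur before the first study dose and under masking, so they should not depend on arm. Protocol 12.4 keeps children who stop study treatment in follow-up and in the ITT analysis. Losses can loosen balance by chance; the plan gives no ground for calling that bias.
- **Imbalance could move the result materially.** Ten extra high-risk children in one arm, with a 12-point risk gap, would shift the difference by 10/336 x 12 = 0.36 points, or 7% of the margin. Neither input comes from the documents. Blocks of four cap imbalance at two children per list at randomisation. Simulating 746 children with the mix above and 10% random loss, an imbalance of ten arose in any single list in fewer than 1% of trials, and across a whole fever category in about 9% to 16%. Such a shift is chance variation that the crude standard error already covers.

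**Conclusion.** The point holds as a small matter of efficiency and chance imbalance. The primary difference and its limit ignore the factors used to randomise, and no planned analysis supplies an adjusted version on the risk-difference scale. Over the assumed stratum rates, the gain in power is about 0 to 1 point at 336 per arm. Type I error is essentially unchanged for no to strong heterogeneity (differences of 0.1 to 0.2 points) and 0.7 points higher with Sato variance in the extreme case.

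A reader might infer that the crude limit is invalid or makes a false claim of non-inferiority more likely. It does not: its simulated error falls from 5.4% to 4.8% as the strata become more different. The size of the gain rests on a 5% mean failure rate and on stratum rates and proportions that had to be assumed. The finding that the plan is unstratified rests only on its text.

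**What to change.** - **SAP 4.2.2 and Tables 3 and 4:** prespecify a stratified risk difference by site, fever and originally prescribed antibiotic, using Mantel-Haenszel weights with Sato variance or a stratified score limit. Compare its one-sided 95% upper limit with 0.05.
- **Pooling rule:** state before unblinding how sparse antibiotic strata are combined, based only on blinded counts. One possibility is TMP-SMX against the beta-lactams. The rule should also place children in the retired amoxicillin-clavulanate stratum.
- **Supporting line:** report the crude difference and limit beside the stratified result, so that the link to the sample-size calculation stays visible.
- **Interim limit (SAP 4.1):** using the same method is optional, since only about half the failures will be available.

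If the crude analysis is kept as primary, the minimum is a sentence giving the reason and a named stratified sensitivity analysis.

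The cost is a few lines of SAP text and a small program change, with no new data. The downside is some dependence of the result on the pooling rule, which is why it must be fixed in advance.
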